#### 8. DATA SOURCES

As this is a NIS, no diagnostic or monitoring procedures additional to the standard of care and routine practice (except for the additional education delivered to the experimental group) will be applied to the patients. All the assessment will be performed by the investigator if they are deemed necessary for the medical treatment procedure.

This study will collect the data from medical charts and MMAS-8 questionnaires. Investigators or delegated site staffs will record the data on the CRF. Data source includes questionnaires, hospital discharge files, abstracts of primary clinical records, electronic medical records, clinical databases, administrative records such as eligibility files, prescription drug files, biological measurements, exposure/work history record reviews, etc.

#### 9. DATA MANAGEMENT AND SOFTWARE/TOOLS

Data collection is the responsibility of the clinical trial staff at the site under the supervision of the principal investigator. During the study, the investigator must maintain complete and accurate documentation for the study.

Designated CRO will serve as the statistical and data coordinating center for this study and will be responsible for data management, quality review, analysis, and reporting of the study data.

The data from enrolling patients in this study will be recorded on a CRF or other applicable forms. The designated CRO will capture, check, store, and analyze the data. The designated CRO will follow Boehringer Ingelheim standard operating procedures (SOPs) and their own internal SOPs.

A data management plan (DMP) will be created to describe all functions, processes, and specifications for data collection, cleaning, and validation. Validation process will be performed as outlined in a data validation plan (DVP). Queries will be reviewed and sent to the study investigators for clarification. Designated site staffs for investigation are required to reply the queries and make any necessary changes to the data. The queries will be resolved and data will be updates under the agreement of investigator. Once all queries have been resolved, the database will be locked. The locked data will be exported to generate the subject listings, tabulations, and statistical analyses.

Data will be transferred to Boehringer Ingelheim after the closure of the study.

#### 9.1 Software/Tools

The data collected will be entered into the study database against the paper CRF. The data will be further exported to Statistical Analysis System® (SAS) for Windows (Version 9.4 or higher, SAS Institute, Cary, North Carolina, USA) to generate the subject listings, tabulations, and statistical analysis.

#### 9.2 Handling of Missing Values

No imputation method will be performed to estimate the missing values for all the study variables.

#### 9.3 Handling of Inconsistencies in Data and Outliers

Data validation plan will be developed to define validation rules for all the collected data in this study. Data manager will perform the validation process based on validation plan to clarify the inconsistencies if any. The extremely high and/or low value of laboratory data need to be marked as abnormal in CRF. Statistician will perform ST review prior to data lock to identify if any possible wrong values. Query will be generated for the questionable data and site staff need to clarify the data to make sure it is consistent with the source document. No other statistical methods will be performed to modify or exclude the inconsistencies and outliers.

#### 10. DATA ANALYSIS

The main and further analysis population will consist of all eligible patients (i.e., all patients who have signed the informed consent and have fulfilled all eligibility criteria).

Continuous variables will be reported as number, mean, standard deviation (SD), minimum, maximum, and 95% confidence interval (CI). Categorical variables will be summarized as number and frequency or percentage with observed (non-missing) data. Missing numbers of both continuous and categorical variables will also be summarized.

As for comparisons of continuous data between baseline and follow-up visit, paired-t test will be performed at the significant level of 0.05. Shapiro—Wilk test will be performed to test the normality of data. When normality assumption is violated, Wilcoxon signed-rank test will be performed instead. On the other hand, McNemar's test will be performed to for comparisons of categorical data between baseline and follow-up visit at the significant level of 0.05.

For the endpoints pre-identified to compare between patients with and without advanced educational intervention, the analyses will be done by independent t-test for continuous data at the significant level of 0.05. Shapiro–Wilk test will be performed to test the normality of data. When normality assumption is violated, Wilcoxon rank-sum test will be performed instead. On the other hand, Chi-square or Fisher's exact test will be performed to for comparisons of categorical data at the significant level of 0.05.

#### 10.1 Main analysis

The primary outcome is to describe the proportion of patients with high adherence to dabigatran treatment which is defined as achieving MMAS-8 score of 8 points at 12 months for each group.

• The proportion of patients with high (MMAS-8 score: 8 points) adherence to dabigatran treatment at x months ( $P_{H,x}$ ) is defined as following formula:

$$P_{H,x} = \frac{\text{Number of subjects with 8 points of MMAS} - 8 \text{ score at x months}}{\text{Number of subjects at x months}}$$

Subjects without MMAS-8 value recorded at 12 months will be excluded from the analysis of primary endpoint. The Chi-square test or Fisher's exact test will be used to test the equality between two study groups.

The secondary analyses are described below:

- (1) The proportion of patients with high (MMAS-8 score: 8 points) adherence to dabigatran treatment at each visit (3, 6, and 9 months),
- (2) The proportion of patients with medium (MMAS-8 score: 6-7 points) and low (MMAS-8 score < 6 points) adherence to dabigatran treatment at each visit (3, 6, 9 and 12 months),
- (3) The mean MMAS-8 score at each visit (3, 6, 9 and 12 months) and
- (4) The discontinuation rate of dabigatran and reasons for discontinuation (switch or stop treating dabigatran).

Similar as primary endpoint, Chi-square test or Fisher's exact test will be used to test the equality of MMAS-8 score, discontinuation rate and reasons for discontinuation between two

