9. RESEARCH METHODS

9.1 STUDY DESIGN

This is a multi-center, 1:1 randomized study to evaluate the effects of educational intervention on adherence to dabigatran, for up to 12 months. The study will be carried out at around 20 hospitals (20 ± 3), where AF patients are mainly treated in Taiwan. A total of 1,200 patients are planned to be enrolled to target 1,000 patients included in the analysis.

Patients newly diagnosed with AF within 1 month, under 75 years old, and newly prescribed with dabigatran on physician's decision per local labelling will be enrolled and equally randomized to receive standard of care (routine clinical practice) or standard of care (routine clinical practice) with advanced educational intervention. To create the randomization numbers, we will use block randomization by Statistical Analysis Software (SAS®) Version 9.4 or higher (SAS Institute, Cary, NC, USA).

The study duration consists of a 1-year enrolment period and a 12-month follow-up period consisting of visits at 3, 6, 9, and 12 months for each individual patient. Being an NIS, the time points of follow-up visits are set in accordance with the routine outpatient follow-ups of AF management in Taiwan. Patients will be continuously followed until death, lost to follow-up, or end of data collection at 12 months, whichever comes first.

The educational materials from "Shared decision making of treatment of NOAC in AF patients" (NTA: 180647) and "Atrial Fibrillation Patient Care in Hospitals" (NTA: 190707) will be used as the educational materials for the experimental group. The education materials will be delivered after randomization (baseline); and at 3, 6, and 9 months thereafter. The adherence to dabigatran will be measured by MMAS-8 score at 3, 6, 9, and 12 months.

The comorbidities, VASc score, and HAS-BLED score will be recorded at baseline; and at 3, 6, 9, and 12 months. Stroke, thromboembolic events, and bleeding-related events will also be captured during 12 months of follow-up.

The whole NIS will be implemented by a Contract Research Organization (CRO) under Local Boehringer Ingelheim's governance.

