9.3 VARIABLES

9.3.1 Exposures

Being an NIS, the prescription of dabigatran will be in accordance with the Summary of Product characteristics and physician's discretion. Treatment record of dabigatran will be collected and recorded on CRF across the 12 months of study period. Data to be collected include start/end date of administration, dose, and the reason for dose adjustment or interruption.

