9.3.2.2 Secondary outcomes

- (1) The proportion of patients with high adherence to dabigatran treatment which is defined as achieving the MMAS-8 score of 8 points at 3, 6, and 9 months in patients with and without advanced educational intervention
- (2) The proportion of patients with medium (MMAS-8 score: 6-7 points) and low (MMAS-8 score < 6 points) adherence to dabigatran treatment at 3, 6, 9, and 12 months in patients with and without advanced educational intervention
- (3) The mean MMAS-8 score at 3, 6, 9, and 12 months in patients with and without advanced educational intervention
- (4) The discontinuation rate of dabigatran and reasons for discontinuation (switch or stop treating dabigatran) in patients with and without advanced educational intervention

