9.5 STUDY SIZE

Approximately 1,200 patients from around 20 hospitals (20 ± 3) will be enrolled in this study. Assuming a drop-out rate of 20%, it is expected to have 1,000 patients completing the study. The sample size is determined based on the feasibility, planned enrolment period, number of potential patients at selected sites, and expected precision of the estimates. As the selected sites are the hospitals with most AF patients treated with dabigatran in Taiwan from northern to southern areas, the patients recruited into this study will be the representative of the AF population treated with dabigatran and the healthcare settings in Taiwan.

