9.7.1 Main analysis

The analyses will be mainly descriptive to gain an understanding of the characteristics of the sample studied.

Continuous variables will be reported as number, mean, standard deviation (SD), minimum, maximum, and 95% confidence interval (CI). Categorical variables will be summarized as number and frequency or percentage with observed (non-missing) data.

Analysis of endpoints:

- The primary outcome is to describe the proportion of patients with high adherence to dabigatran treatment which is defined as achieving MMAS-8 score of 8 points at 12 months for each group. Subjects without MMAS-8 value recorded at 12 months will be excluded from the analysis of primary endpoint.
- The Mean MMAS scores at 3, 6, 9 and 12 months will be compared between patients with and without advanced educational intervention using Chi-square, Fisher's exact, or other appropriate tests for categorical data and using t-test or Wilcoxon rank-sum test for continuous data. Similarly, subjects without MMAS-8 value recorded at a specific visit will be excluded from the analysis of corresponding secondary endpoints.
- Other secondary outcomes in patients with and without advanced educational intervention separately and further outcomes only within pooled patient set (e.g., comorbidities, stroke/thromboembolic/bleeding events, risk factors, ADR, etc.) will all be analyzed in a descriptive manner
- All tests will be done under a statistical level of 0.05.

NIS Protocol Page 33 of 46

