#### 6. RESEARCH METHODS

#### 6.1 STUDY DESIGN

This is a multi-center, 1:1 randomized study to evaluate the effects of educational intervention on adherence to dabigatran, for up to 12 months. The study will be carried out at around 20 hospitals ( $20 \pm 3$ ), where AF patients are mainly treated in Taiwan. A total of 1,200 patients are planned to be enrolled to target 1,000 patients included in the analysis.

Patients newly diagnosed with AF within 1 month, under 75 years old, and newly prescribed with dabigatran on physician's decision per local labelling will be enrolled and equally randomized to receive standard of care (routine clinical practice) or standard of care (routine clinical practice) with advanced educational intervention. To create the randomization numbers, we will use block randomization by Statistical Analysis Software (SAS®) Version 9.4 or higher (SAS Institute, Cary, NC, USA).

The study duration consists of a 1-year enrolment period and a 12-month follow-up period consisting of visits at 3, 6, 9, and 12 months for each individual patient. Being an NIS, the time points of follow-up visits are set in accordance with the routine outpatient follow-ups of AF management in Taiwan. Patients will be continuously followed until death, lost to follow-up, or end of data collection at 12 months, whichever comes first.

The educational materials from "Shared decision making of treatment of NOAC in AF patients" (NTA: 180647) and "Atrial Fibrillation Patient Care in Hospitals" (NTA: 190707) will be used as the educational materials for the experimental group. The education materials will be delivered after randomization (baseline); and at 3, 6, and 9 months thereafter. The adherence to dabigatran will be measured by MMAS-8 score at 3, 6, 9, and 12 months.

The comorbidities, VASc score, and HAS-BLED score will be recorded at baseline; and at 3, 6, 9, and 12 months. Stroke, thromboembolic events, and bleeding-related events will also be captured during 12 months of follow-up.

The whole NIS will be implemented by a Contract Research Organization (CRO) under Local Boehringer Ingelheim's governance.

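### The primary endpoint has no rule for patients no longer on dabigatran at 12 months, so it can show, halve, hide or reverse an effect on staying on the drug

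*SAP*

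**What the plan says.** The objective is to explore whether education improves adherence to dabigatran over 12 months (Protocol 8, SAP 5). SAP 10.1 turns this into the proportion with "high adherence to dabigatran treatment which is defined as achieving MMAS-8 score of 8 points at 12 months for each group". The numerator is the number of subjects scoring 8 and the denominator the number of subjects at that visit. Subjects with no score at 12 months are excluded, and SAP 9.2 rules out imputation. The arms are compared by chi-square or Fisher's exact test.

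Follow-up does not depend on staying on the drug: "Patients will be continuously followed until death, lost to follow-up, or end of data collection at 12 months, whichever comes first" (Protocol 9.1). Neither switching nor stopping dabigatran is among the listed reasons for leaving the study (Protocol 9.2.2.3). Both are expected, because secondary outcome 4 covers the discontinuation rate and "reasons for discontinuation (switch or stop treating dabigatran" (Protocol 9.3.2.2). The Month 12 visit asks for the MMAS-8 without condition (Protocol 9.2.3.5). The analysis population is all eligible patients (SAP 10).

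The information needed to identify these patients is on the CRF: "Data to be collected include start/end date of administration, dose, and the reason for dose adjustment or interruption" (Protocol 9.3.1). SAP 7.1.1 already derives treatment duration from those dates.

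**The concern.** The endpoint is named for adherence to dabigatran but calculated from a score alone. A patient no longer on dabigatran at month 12 either contributes a raw score or, if the score is blank, drops out of the comparison. Neither outcome records that the patient is off the drug. Dropping the patient also conditions a randomised comparison on a post-randomisation event that the education may influence.

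Neither document tells a site whether such a patient completes the questionnaire, or about which medicine. Two sites could handle the same patient differently and both comply. SAP 11 holds the biostatistician to the methods as written, so the gap is not left to judgement at analysis. At stake is whether the primary comparison reflects an effect of education on remaining on dabigatran.

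**Working it through.** **Plan's own figures.** The plan states no power, effect size or discontinuation rate, so there is no primary-endpoint figure to reproduce. The only sample-size figures are enrolment ("Approximately 1,200 patients from around 20 hospitals") and 1,000 completers at 20% drop-out. In fact 1,200 × 0.80 = 960. That mismatch is a separate matter, so 480 and 500 per arm are both used. Allocation is 1:1 and the level 0.05 ("All tests will be done under a statistical level of 0.05"), taken as two-sided because sidedness is not stated.

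**Inputs.**
- h = probability of scoring 8 while on dabigatran: 71% in both arms. This is the high-adherence rate in the US study described in Protocol 7, used only as an illustration.
- d = share off dabigatran at month 12: assumed.
- hs = probability that an off-drug patient who answers scores 8: assumed, and equal in both arms.
- s = share of off-drug patients who have a score.

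**Formulas.**
- Plan: P = [(1 − d)h + d·s·hs] / [(1 − d) + d·s].
- If all answer (s = 1), education minus control = (d_control − d_education) × (h − hs). The sign and size depend on hs, which the plan leaves open.
- If all are blank (s = 0), or if hs = h, then P = h whatever d is.
- Score of 8 and on dabigatran: P = (1 − d)h.

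**Results under the plan.**

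| Off drug, control v education | Off-drug patients | Control | Education | Difference (points) |
|---|---|---|---|---|
| 20% v 10% | score 8 at 71% | 0.568 + 0.142 = 71.0% | 0.639 + 0.071 = 71.0% | 0 |
| 20% v 10% | all blank | 0.568/0.80 = 71.0% | 0.639/0.90 = 71.0% | 0 |
| 20% v 10% | score 8 at 35.5% | 0.568 + 0.071 = 63.9% | 0.639 + 0.0355 = 67.5% | +3.55 |
| 20% v 10% | none scores 8 | 56.8% | 63.9% | +7.1 |
| 30% v 15% | score 8 at 90% | 0.497 + 0.270 = 76.7% | 0.6035 + 0.135 = 73.9% | −2.85 |
| 30% v 15% | score 8 at 50% | 0.497 + 0.150 = 64.7% | 0.6035 + 0.075 = 67.9% | +3.15 |
| 30% v 15% | none scores 8 | 49.7% | 60.4% | +10.65 |

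**Results with the drug condition.** The proportions no longer depend on hs or s.
- 20% v 10% off drug: 56.8% v 63.9%. At 480 per arm the pooled proportion is 0.6035, so z = 0.071 / √(0.6035 × 0.3965 × 2/480) = 2.25. Power is 61% (63% at 500 per arm). Where the plan gives 71% v 71%, the rejection rate is 5%.
- 30% v 15%: 49.7% v 60.4%, power 91% (92% at 500).
- 15% v 10%: 60.4% v 63.9%, z = 1.13 and power 20% at 480 per arm. A small difference in persistence would usually be missed under either definition.

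**Patients affected.** At 20% v 10% off drug and 480 per arm, 96 + 48 = 144 of 960 patients (15%) would have no stated classification.

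**The case against.** A reader might infer that a score of 8 earned on another anticoagulant counts as high adherence to dabigatran. The documents do not say so. Protocol 9.3.2.4 and SAP 7.1.2.1 describe the MMAS-8 as evaluating adherence to dabigatran, and the questionnaire is a stand-alone document (Protocol Annex 1) that is not shown. The same sections say that the instrument picks up stopping medicines on one's own initiative, so some patients who stopped may score below 8 and be classified as one would wish. If all off-drug patients did so, the plan's formula would hide nothing. This part of the objection stands: the masking is possible, not established.

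The plan does not ignore persistence either. SAP 10.1 tests the discontinuation rate and reasons between arms, so fewer stops or more switches would be visible there. That stands too, but it does not tell the reader what the primary proportion means. Describing medication-taking separately from discontinuation is also defensible. However, that would require restricting the score to patients on the drug and saying so, and the plan does neither.

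The objective is exploratory and the analyses mainly descriptive, which lowers the severity. Even so, the study is randomised, and the SAP tests the primary proportion between arms.

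A reader might also infer from the title of one education document ("Shared decision making of treatment of NOAC in AF patients") that education itself changes switching. Only titles are given, so this has no support, and the point does not need it.

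**Conclusion.** The point holds as a gap in the endpoint definition. Nothing in the available text says how patients off dabigatran are scored or classified in P_H,12. Some SAP text is not shown, including most of page 18, and could not be checked.

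Under the assumed 20% v 10% off drug, the plan's difference ranges from 0 to 7.1 points depending only on how off-drug patients are scored. At 30% v 15%, with 90% of off-drug patients scoring 8, it reverses to 76.7% v 73.9%, favouring control although education halved discontinuation. All of this rests on assumed off-drug rates, an illustrative 71%, no effect of education on the score itself, and an off-drug scoring rate that is the same in both arms. It shows what the rule permits and does not predict the result.

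This should be fixed, with medium confidence, because a score-only formula followed literally can hide or reverse a persistence effect in the primary comparison.

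**What to change.** In SAP 10.1 and Protocol 9.3.2.1, define high adherence to dabigatran at visit x as an MMAS-8 score of 8 and dabigatran ongoing at that visit by the CRF start and end dates. Keep patients with a recorded switch or stop before visit x in the denominator as not highly adherent, whether or not a score exists. Apply the same rule at months 3, 6, 9 and 12. Patients with no recorded switch or stop and no score stay under the existing missing-score rule.

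Report the score-only proportion as supplementary. For it to be interpretable, state whether off-drug patients complete the MMAS-8 and about which medicine. Where the recorded reasons allow, add a version that sets aside physician-directed stops. The documents describe no such reason category, so check first that the CRF captures it.

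The cost is a change of wording in both documents and one derived variable from dates already collected. The reported proportion will be lower, and medically directed stops will count as failures in the main version. The supplementary versions show how much that matters.

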## Statistical Analysis Plan (SAP) for Non-Interventional Studies (NIS) BI Study Number 1160-0304

Page 12 of 27

- The educator delivers advanced education to subjects in the experimental group.
- Record the use of dabigatran (dose, date of administration)
- Record the concomitant therapies for AF or stroke prevention within 1 month prior to the baseline (generic name or name of the therapy)
- Record the occurrence of stroke and thromboembolic events, if any
- Record the occurrence of bleeding-related events, if any
- Do safety reporting if any dabigatran relevant ADR, fatal AEs, and pregnancies occurs

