#### 7.1.3 Covariates

Patients recruited will be evaluated for covariates at the visit of baseline. Potential confounders include demographics (age, gender, race, and educational level), VASc score, HASBLED score, comorbidities, concomitant therapies, dose of dabigatran, and renal function.

Statistical methods will be performed to test the difference of covariates between the study group at the visit of baseline (please referred to section 10. data analysis). If any significant difference occurred, linear regression will be conducted to model the relationship between dependent variable and all explanatory variables.

As for linear regression model, the primary endpoint (MMAS-8 score at 12 months) will be considered as dependent variable, and all covariates listed above including study group variable will be considered as explanatory variable.

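### The plan does not say whether randomisation blocks are formed within hospital, and the primary test pools about 20 hospitals; the cost is lost precision, not loss of validity

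*SAP*

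**What the plan says.** SAP 6.1 describes the design: "This is a multi-center, 1:1 randomized study". Protocol 9.1 adds "The study will be carried out at around 20 hospitals", with a tolerance of 3 either way. On allocation, both documents give the software and the method: "To create the randomization numbers, we will use block randomization by Statistical Analysis Software". They name no stratification factor and no block size, and do not say whether there is one list or one per hospital.

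The primary analysis in SAP 10.1 compares the two arms as a single 2 × 2 table: "The Chi-square test or Fisher's exact test will be used to test the equality between two study groups". Protocol 9.7.1 sets the level: "All tests will be done under a statistical level of 0.05".

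The only adjusted model is in SAP 7.1.3, and it is conditional on baseline testing: "If any significant difference occurred, linear regression will be conducted to model the relationship between dependent variable and all explanatory variables". Its covariates are demographics, risk scores, comorbidities, concomitant therapies, dabigatran dose and renal function, plus study group. Hospital is not among them.

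On delivery, the SAP visit descriptions say "The educator delivers advanced education to subjects in the experimental group". The documents do not say how many educators there are or how they are assigned to hospitals.

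**The concern.** Routine counselling and the way a questionnaire is completed can differ between hospitals, so hospital is a plausible predictor of scoring 8. An analysis usually reflects the factors used in the randomisation and uses strong, freely available predictors. Here the reader cannot tell whether hospital was a randomisation factor, and the primary test does not use it in either case.

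There are two possibilities. If blocks are formed within hospital, the pooled test ignores the strata and its standard error is too large. If one list serves all hospitals, arm sizes within a hospital are left to chance, and between-hospital variation stays in the error term. Both reduce the chance of detecting a real education effect. A single pooled result also says little about whether the effect holds across hospitals.

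**Working it through.** **The plan's own figure.** No power, effect size or hospital variance is stated. The only sample-size figure is 1,200 enrolled, 20% drop-out and 1,000 analysed (Protocol 9.5). Strictly, 1,200 × 0.80 = 960, but this is a separate matter and hardly affects the present point: pooled-test power for 71% versus 79% is 0.833 with 500 per arm and 0.818 with 480. The calculations below use 1,000.

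**Inputs**
- From the documents: 20 hospitals, 1:1 individual randomisation, level 0.05, 1,000 analysed.
- Control rate 71%: the dabigatran rate from the US study cited in Protocol section 7, used here as an assumption.
- Assumed: two-sided testing; 79% with education; hospital intraclass correlation (ICC, the share of outcome variance lying between hospitals) of 0 to 0.10.

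**Type I error, by formula.** The pooled test takes the outcome variance as p(1 − p). If blocks are formed within hospital, only the within-hospital part, p(1 − p)(1 − ICC), affects the arm difference. The true size is therefore 2 × [1 − Φ(1.96 / √(1 − ICC))].
- ICC 0.02: 1.96 / 0.990 = 1.980, size 4.8%
- ICC 0.05: 1.96 / 0.975 = 2.011, size 4.4%
- ICC 0.10: 1.96 / 0.949 = 2.066, size 3.9%

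With one common list, hospital is randomised along with the patient, so the between-hospital variance belongs in the error term and the size stays near 5%.

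**Simulation.** There were 6,000 trials per setting, with 20 hospitals of 50 analysed patients. The education effect is a constant log odds ratio of ln(0.79/0.21) − ln(0.71/0.29) = 0.43. CMH is the Cochran-Mantel-Haenszel test stratified by hospital. Simulation error is about 0.003 for size and 0.005 for power.

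| List | ICC | Size, pooled | Size, CMH | Power, pooled | Power, CMH |
|---|---|---|---|---|---|
| One list | 0 | 0.051 | 0.051 | 0.837 | 0.832 |
| One list | 0.02 | 0.053 | 0.056 | 0.823 | 0.821 |
| One list | 0.05 | 0.048 | 0.049 | 0.801 | 0.811 |
| One list | 0.10 | 0.049 | 0.048 | 0.753 | 0.787 |
| By hospital | 0 | 0.047 | 0.047 | 0.840 | 0.841 |
| By hospital | 0.02 | 0.046 | 0.048 | 0.816 | 0.821 |
| By hospital | 0.05 | 0.038 | 0.043 | 0.805 | 0.815 |
| By hospital | 0.10 | 0.041 | 0.051 | 0.773 | 0.801 |

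The comparison to make is across a row. Part of the fall in power down the table arises because a fixed odds ratio gives a smaller overall risk difference when hospitals vary.

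Across rows, the gain from CMH is nil within simulation error at ICC 0 to 0.02, about 1 point at 0.05 and about 3 points at 0.10 (0.787 − 0.753 = 0.034; 0.801 − 0.773 = 0.028). Changing both list and test at ICC 0.10 gives 0.801 − 0.753 = 0.048, about 5 points. Unequal hospitals of 7 to 150 patients give the same pattern. A separate simulation put the gain from CMH at about 7 points at ICC 0.19.

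**Chance imbalance under one list.** With 1,200 / 20 = 60 patients per hospital, the number in one arm has SD √(60 × 0.25) = 3.87, so its 95% range is 30 ± 7.6, about 22 to 38. In the simulation with 50 per hospital, the median of the largest within-hospital arm difference was 14 patients under one list and 0 with stratified lists.

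**The case against.** The strongest reply is that nothing invalid is planned. Individual randomisation protects the pooled test, the study is described as exploratory and mainly descriptive, no power claim is made, and the loss is small at modest ICCs. This stands, and it limits the point to efficiency and clarity. It does not remove it: SAP 10.1 specifies a formal between-arm test of the primary endpoint at 0.05, and the SAP's stated purpose is to give the full statistical methodology.

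It is also fair that the mock-up tables mentioned in SAP section 3 are not available here and that Protocol 9.7 allows further exploratory analyses. A by-hospital display may therefore already be planned. The gap established here is confined to the stated primary test and the visible model.

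A reader might infer three stronger things that the documents do not support.
- *Randomisation ignores hospital.* The text is silent on list structure, and blocks may well be issued per hospital.
- *Each hospital has its own educator, and educator differences should be balanced between arms.* Educator numbers and assignment are not given. Educators act only in the education arm, so their differences are part of the intervention effect and cannot be balanced. Two common sets of materials are used throughout.
- *Educator variation inflates the false-positive rate of the planned test.* With an assumed between-educator SD of 0.2, 0.4 or 0.6 on the logit scale, ICC 0.05 and equal hospitals, the pooled test under one list rejects in about 6%, 11% and 16% of trials. That concerns a zero average effect over a wider population of educators with real effects at individual hospitals, not the hypothesis of no effect that the SAP tests. Stratification does not change it: blocks by hospital with CMH give about 6%, 10% and 17%.

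**Conclusion.** The point holds as a matter of precision and specification. The plan does not state whether blocks are formed within hospital. The primary test pools about 20 hospitals, and no visible planned model includes hospital. The pooled test does not gain false positives from hospital differences: its size stays near 5% with one list and falls to about 4% at ICC 0.05 to 0.10 with blocks by hospital. The cost of pooling is about 0 to 3 points of power for ICC 0 to 0.10, and more above that.

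These sizes rest on an assumed 71% versus 79%, 1,000 analysed patients and assumed ICCs. A smaller ICC would make the gain negligible. The change is worth making because it is cheap, not because the planned result would be misleading.

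**What to change.** - **Protocol 9.1 and SAP 6.1:** specify permuted blocks stratified by hospital. If the list already exists, state the structure that was used.
- **SAP 10.1:** replace the pooled chi-square or Fisher test of the primary endpoint with a Cochran-Mantel-Haenszel test stratified by hospital. Report the stratified risk difference with its 95% confidence interval. Set a rule in advance for combining small hospitals.
- **Optional sensitivity analyses:** a by-hospital display and a model with a random hospital-by-arm term. These address whether the effect generalises across hospitals or educators; they do not correct the type I error of the planned test.

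The cost is SAP wording and some programming. No extra patients or data are needed, and the analysis change remains possible after randomisation because each patient's hospital is known. The small downside is the rule for combining small hospitals, which must be fixed before the data are analysed.
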